14 DATA HANDLING AND RECORD KEEPING

14.1 Data Handling

14.1.1 Case Report Forms

The Sponsor or designee will provide an EDC (Electronic Data Capture) system to allow data entry by site users.

Each member of the site will be assigned a username, a personal login and a password to enter into the EDC system.

The investigator will be responsible for the timeliness, completeness and accuracy of the information in the eCRF (Electronic Case Report Form).

Data will be entered according to the chronological sequence provided for in the eCRF.

All study-specific source data must be maintained on-site, kept in a file per subject.

Changes to information in the source documents will be initialed and dated and reason for change documented by the person making the change.

Copies of de-identified crucial source data will be delivered to the Sponsor. Such crucial source data includes copies of all reports (VTP Report Form, TOOGUIDE TRUS report, ...), laboratory reports and other relevant documents. In these cases, the subject's identification will be kept confidential and will be limited to initials and subject identification number in the Study.

14.1.2 Data Accrual and Entry

The data will be entered by the Investigator or his/her delegate into the eCRF on an ongoing basis, ensuring all relevant items are completed, there is no missing data and that all data entered are consistent with the source documentation.

Data will be entered according to the data entry instructions provided.

The data will be electronically verified through use of automatic checks during data entry, SAS programmed edit checks to check complex conditions (if any) and data monitoring.

Data correction will be made by site users.

An audit trail will identify the person entering/correcting the data, date and time of data entry and reason for correction.

14.1.3 Coding

Any previous medication (started before the screening visit) and concomitant medication (started at the screening visit or up to the last visit) will be encoded by using the current version of the WHO drug dictionary and medical conditions will be encoded by using the current MedDRA version.

14.1.4 Data Transfer

Final validated data will be recorded in SAS® data sets and sent to the Sponsor.

14.1.5 Final Report

A final study report will be written in English. The report will give full experimental details of the clinical and analytical phases of the study.

The reports will comply with all the requirements and recommendations described in guidelines ICH E3.

14.2 Retention of Study Records

The investigator is ready to receive and cooperate with any auditor designed by the Sponsor to ascertain the performance of the study according to ICH GCP (17, 18, 19, 20, 21).

Archiving will be carried out at the clinical sites in an appropriate room designed for record retention. This room is locked around the clock, and includes fire detection monitoring.

The investigator will retain originals of the approved project protocol, subjects' participation agreements, relevant source documents will be kept per institutional guidelines and GCP and all other supporting documentation related to the project. He/she must make these files available for inspection by an authorized representative of the Sponsor or the regulatory authorities upon reasonable request. Complete CRFs have to be collected by the Sponsor at the end of the study.

All study-related records, including source documents, CRFs, and regulatory documents, must be retained as outlined in the ICH guideline for Good Clinical Practice. These documents should be retained for a longer period if demanded by regulatory requirements or by an agreement with the Sponsor.

The on-site Investigator is responsible for the retention of all study documents for the appropriate period, and must inform the Sponsor in writing of any change in the status of these documents.

The Sponsor will inform the Investigators in writing when these documents no longer need to be retained.

15 FINANCING AND INSURANCE DOCUMENTATION

Steba Biotech S.A. insurance contracts will cover the study.

16 PUBLICATION POLICY

The Sponsor or its designee will submit an ICH-compliant clinical study report to the Primary Investigator at the conclusion of the study. The contents of this report will include: study objectives, methods (including any deviation from the study protocol), evaluation of the study results, observations by the Primary Investigator regarding the value of the study drug, and a discussion of all AEs with interpretation by the Primary Investigator regarding study drug involvement.

All information concerning the tested drug and the Sponsor's operation, such as patent applications, formulae, manufacturing processes, basic scientific data and formulation information supplied by the Sponsor and not previously published are considered confidential, shall be not disclosed and shall remain the sole property of the Sponsor. The investigator agrees to use such information only within the completion of the study and will not use it for other purposes without prior written consent from the Sponsor.

It is understood by the Investigator that the information from the clinical study will be used by the Sponsor in connection with the development of the tested drug, and therefore may be disclosed as required to other clinical Investigators or to government agencies. In order to allow for the use of the information derived from the clinical studies, it is understood and agreed that there is a commitment to provide the Sponsor with complete test results and all data developed in the study. The investigator further recognizes that the disclosure of such confidential information may destroy the commercial value of the tested drug.

Disclosure of the results and all data developed in the study by the investigator for publication will not be unreasonably withheld by the Sponsor except as required for patent protection. Where the Protocol is part of a multicentre study, the investigator agrees to withhold publication or presentation of data until the date of the publication or presentation by the Sponsor of the multicentre data in full.

The information in this and any further documentation contains trade secrets and commercial information that are privileged or confidential and may not be disclosed unless such disclosure is required by law or regulations.

In any event, the individuals to whom the information is disclosed must be informed that the information is privileged or confidential and may not be further disclosed by them.

## Explanation

**LIST OF ABBREVIATIONS**

Abbreviation or special term	Explanation
AE	Adverse Event
ATC	Anatomical Therapeutic Classification
BMI	Body Mass Index
CRF	Case Report Form
CTC	Common Terminology Criteria
ECG	Electrocardiogram
IIEF	International Index of Erectile Function
IPSS	International Prostate Symptom Score
LDI	Light Density Index
MedDRA	Medical Dictionary for Regulatory Activities
MRI	Magnetic Resonance Imaging
NCI	National Cancer Institute
OC	Observed Cases
PP	Per Protocol
PSA	Prostate Specific Antigen
SAE	Serious Adverse Event
SAP	Statistical Analysis Plan
SD	Standard Deviation
SE	Standard Error
SOC	System Organ Class
TNM	Tumor Node Metastasis
TRUS	Trans Rectal Ultrasound
VAS	Visual Analogue Scale
VTP	Vascular-Targeted Photodynamic therapy
WHO	World Health Organization

## Introduction

The purpose of this statistical analysis plan (SAP) is to provide an analytic framework, which addresses analyses in support of the protocol objectives. This analysis plan is based on the protocol of the PCM204 study as protocol version 6.0 dated 1st October 2018 (MSKCC IRB# 17 070(2)).

## Study Objectives, endpoints and Design

### Objectives

#### Primary objective

The primary objective of the study is to evaluate for the absence of biopsy detectable Gleason grade 4 or 5 prostate cancer on 12- month, post-treatment biopsy following TOOKAD® Soluble- VTP in men with Gleason score 7 (3+4) prostate cancer.

#### Secondary objectives

The secondary objectives of the study are:

1. To describe the rate of responders, with response defined as the absence of any Gleason pattern 4 or 5 biopsy on or before months 24, 36, 48 and 60. If a subject is retreated following a positive biopsy at 3 months and subsequent biopsy shows absence of Gleason pattern 4 or 5, the subject will be considered to have responded
2. To describe the rate of responders, with response defined as the absence of any prostate cancer on biopsy on or before months 3, 12, 24, 36, 48 and 60. If a subject is retreated following a positive biopsy at 3 months and subsequent biopsy shows absence of any cancer, the subject will be considered to have responded
3. To describe the rate of responders, with response defined as the absence of any Gleason grade 4 or 5 biopsy on or before months 12, 24, 36, 48 and 60 in the treated lobe. If a subject is retreated following a positive biopsy at 3 months and subsequent biopsy shows absence of Gleason grade 4 or 5, the subject will be considered to have responded
4. To describe the rate of responders, with response defined as the absence of any prostate cancer on biopsy on or before months 3, 12, 24, 36, 48 and 60 in the treated lobe. If a subject is retreated following a positive biopsy at 3 months and subsequent biopsy shows absence of any cancer, the subject will be considered to have responded
5. To describe the change in biopsy results between 3, 12, 24, 36, 48 and 60 months after TOOKAD® Soluble- VTP.
6. To describe changes in urinary and erectile function and their potential impact on QOL using International Prostate Symptom Score (IPSS) and International Index of Erectile Function (IIEF) questionnaires up to 60 months
7. To describe the occurrence of adverse events of TOOKAD® Soluble VTP treatment in patients with localized prostate cancer
8. To describe the occurrence of severe prostate cancer-related events: cancer extension to T3, metastasis and prostate cancer-related death

9. To document the occurrence of secondary prostate cancer therapies following VTP treatment
10. To describe changes in PSA from blood samples following TOOKAD® Soluble-VTP.

## **Endpoints**

### **Primary endpoint**

The primary efficacy variable is the result of the Month 12 biopsy, in which success is defined by absence of detectable Gleason grade 4 or 5 prostate cancer.

The primary endpoint will be analysed as a dichotomous outcome, i.e., success (absence of any histology result positive for Gleason 4 or 5 prostate cancer at 12 months) or failure (presence of at least one result positive for Gleason grade 4 or 5 prostate cancer at 12 months).

### **Secondary endpoints**

- Binary response to treatment defined as the absence of any Gleason grade 4 or 5 biopsy on or before months 24, 36, 48 and 60. If a subject is retreated following a positive biopsy at 3 months and subsequent biopsy shows absence of Gleason grade 4 or 5, the subject will be considered to have responded
- Binary response to treatment defined as the absence of any Gleason grade 4 or 5 biopsy on or before months 12, 24, 36, 48 and 60 in the treated lobe. If a subject is retreated following a positive biopsy at 3 months and subsequent biopsy shows absence of Gleason grade 4 or 5, the subject will be considered to have responded
- Binary response to treatment defined as the absence of any prostate cancer on biopsy on or before months 3, 12, 24, 36, 48 and 60. If a subject is retreated following a positive biopsy at 3 months and subsequent biopsy shows absence of any cancer, the subject will be considered to have responded
- Binary response to treatment defined as the absence of any prostate cancer on biopsy on or before months 3, 12, 24, 36, 48 and 60 in the treated lobe. If a subject is retreated following a positive biopsy at 3 months and subsequent biopsy shows absence of any cancer, the subject will be considered to have responded
- Changes in biopsy result between 3, 12, 24, 36, 48 and 60 months after the procedure
- Patients' reported outcome measures (PROMs) impairment: urinary symptoms using IPSS and erectile functions using IIEF prior to treatment beginning and then 1, 3, 6, 12, 24, 36, 48 and 60 months after completing treatment.

Quality of life is assessed using validated questionnaires. The IPSS comprises seven questions on the urinary symptoms plus one general question about the QOL related to urinary symptoms, whereas the IIEF comprises 15 questions. For both questionnaires, patients self-rate their responses: for the IPSS, using a six-point scale where 0 indicates 'none' or 'normal', whereas 5 indicates the worst response; for the

IIEF, using a five- or six-point scale where 0 indicates 'no sexual activity', and 5 indicates the best response (questions 1 to 10), or where 1 indicates the worst response and 5 the best response (questions 11 to 15).

- Rate of adverse events following treatment

### ***Study design***

#### **Assessments and study duration**

This is a single center, single-arm, open-label, 60-month follow-up phase IIb clinical trial with assessments at 3, 12, 24, 36, 48 and 60 months.

#### **Planned sample size**

For an assumed true response rate of 83.6%, we can discount a response rate of 70% at a one-sided alpha of 10%, with a power of 80% if we have a sample size of 44 patients.

#### ***Interim analyses***

No interim analysis is planned during the study. However, this does not preclude an analysis of the primary endpoint after all data on this endpoint are available, that is after the last patients have completed the Month 12 visit. No further analysis of the primary endpoint will be done after results of this analysis have been published.

#### **Analysis populations**

##### ***Safety population (Safety)***

The safety population includes all who received any amount of TOOKAD® Soluble or initiated any study treatment related procedure (including initiation of pre-procedure anesthesia). The safety population will be used for all safety endpoints.

##### ***Efficacy population***

The efficacy population will include patients who complied with the protocol for inclusion criteria and exclusion and follow-up received the appropriate dose of TOOKAD® Soluble, LDI and energy delivered and underwent the VTP procedure, receiving the ascribed dose of TOOKAD® Soluble and light, had no major protocol deviations and provided data at the 12 month biopsy. A "major" protocol deviation is defined as one which, in the opinion of the PI, could importantly influence the result of the 12 months biopsy and which is adjudicated before the 12-month biopsy.

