1.4 Synopsis

Name of Sponsor/Company: STEBA Biotech S.A.	Protocol	For National Authority Use Only
Name of Finished Product: TOOKAD® Soluble	No: CLIN1601 PCM204	
Name of Active Ingredient: Padeliporfin/ Palladium Bacteriopheophorbide Monolysotaurine (WST11)	Volume:	
TITLE OF STUDY:		
Study of the Efficacy, Safety and Quality of Life after TOOKAD® Soluble Vascular Targeted Photodynamic therapy (VTP) for Minimally Invasive Treatment of Localized Intermediate Risk Prostate Cancer.		
STUDY CENTRE(S):		
It is expected to involve one single center (Memorial Sloan-Kettering Cancer Center) in the United States of America.		
DEVELOPMENT PHASE: This study is designed as a Phase IIb study		
STUDY RATIONALE		
Based on the positive phase II and phase III studies conducted in the United States, Europe, Canada and Latin America, it is expected that TOOKAD® Soluble VTP treatment as a partial gland ablation modality indicated for localized prostate cancer will result in a significant percentage of patients becoming cancer-free, with minimal change from baseline erectile and urinary function and with a good safety profile. These findings have thus far been consistent across the trials in low volume Gleason 3+3 prostate cancer, a disease considered to be low-risk. Among trial participants in the recently completed Phase III Latin American study (PCM304), where few patients with intermediate-risk Gleason score 3+4 cancer were treated, the results appear similar to those of treated men with Gleason 3+3 disease. Therefore, establishing the safety and efficacy of this procedure specifically in men with localized, intermediate risk prostate cancer is an important research objective to be addressed in this study. Interest in performing this study in the U.S. at a center of excellence will provide rigorous evaluation of the technique and oncologic outcomes as well as detailed study of functional metrics.		
STUDY HYPOTHESIS		

TOOKAD® Soluble Vascular Targeted Photodynamic therapy (VTP), as a partial gland ablation therapy for men with unilateral intermediate risk prostate cancer, will result in the absence of detectable, clinically significant prostate cancer in over 70% of treated men.

PRIMARY OBJECTIVE

To evaluate the absence of biopsy detectable Gleason grade 4 or 5 prostate cancer tumors anywhere in the prostate gland on 12-month, post-treatment biopsy following TOOKAD® Soluble-VTP in men with Gleason score 7 (3+4) prostate cancer.

SECONDARY OBJECTIVES

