2.2.4 Clinical Studies

A phase I study conducted in young healthy male subjects showed that intravenous injections of TOOKAD® Soluble are well tolerated up to the dose of 15 mg/kg.

TOOKAD® Soluble treatment of localized prostate cancer comprises several steps: (i) identification of the target using biopsy; (ii) preparation of a treatment guidance by the urologist using the software TOOGUIDE® TRUS where transrectal ultrasound (TRUS) images of the prostate are used to define the number, position and illumination length of fibers required to treat the target. Fiber's illumination is provided by end diffusers of a preferred length from 1 to 5 cm. This allows light delivery adjustment to the target tissue volume and geometry at a given prostate location.; (iii) transperineal insertion of the conducting optical fibers in the lobe of the prostate to be treated (under general anesthesia); (iv) IV infusion of the photosensitiser TOOKAD® Soluble at a standard dose of 4 mg/kg; (v) activation of the circulating TOOKAD® Soluble by laser light delivered through the conducting optical fibers. The energy delivered per fiber is standardised to 200 J/cm.

The phase II studies conducted in low-risk prostate cancer patients in Europe, Canada and the US have shown a correlation between the total energy delivered and efficacy results, thus allowing the determination of optimal treatment conditions with TOOKAD® Soluble (4 mg/kg, 200 J/cm and light density index [LDI] ≥ 1 , see section 6.2.4 below)²³. Moreover, such studies have shown that TOOKAD® Soluble treatment of localized prostate cancer renders a significant percentage (at least 80%) of patients free from prostate cancer in the treated lobe(s) at follow-up biopsies, with minimally impaired erectile and urinary functions as compared with baseline, and with a good safety profile.²⁴ In the largest study, 83% of the patients treated with optimal treatment conditions who underwent prostate biopsy at 6 months had negative histopathology for prostate cancer in the treated lobe.²⁵

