5.5.5 Stopping Rules

The study medication administration and the light delivery are planned to last no longer than approximately 32 minutes. This time will be precisely monitored. The drug or light administration can be discontinued at any time by the investigator in case of a significant adverse event (AE).

Because this study consists of a single administration of the study medication and a single session of light delivery, there is no need to establish rules for stopping the study treatment during the follow-up period.

The Sponsor may terminate the study at any time in a center:

1. If the investigator is non-compliant with the protocol, the regulatory requirements or the ICH-GCP;
2. If the CRF completion or drug accountability is inadequate, and the investigator is unable to take corrective action in any of these cases;
3. In case of failure to recruit subjects.

The entire study may be terminated for medical reasons. In addition the Sponsor retains the right to end the study at any time if the study cannot be carried out as agreed upon in the study protocol. In case of premature termination the Investigators, IRB/IECs and regulatory authorities will be informed by the Sponsor.

The Sponsor also reserves the right to terminate the study at any time for administrative reasons. The Sponsor will not reimburse the Investigator for the evaluation of subjects if the evaluations are conducted in a manner other than that specified in this protocol.

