6.3.4 Procedures carried out in the operating-room

Light delivery catheter insertion:

Subjects will be placed in the lithotomy position and will remain in this position throughout the procedure. A Foley catheter is placed in the bladder prior to the procedure, and removed at least 6 hours after the procedure. TRUS images are used to visualize the prostate and to define the treatment guidance using TOOGUIDE TRUS.

A transperineal template is used to guide the placement of the flexible hollow introduction catheters into the prostate. These have a metal inner mandrel to aid insertion. This procedure is similar to that used routinely for high dose rate (HDR) brachytherapy of prostate cancer.

Following satisfactory positioning of the introduction catheter the metal mandrel is removed and replaced with a cylindrically diffusing optical fiber. The length of the diffusing part of the fiber is chosen according to the treatment guidance based on the ultrasound images of the prostate. Fibers are available with illuminating fiber lengths of 1 - 5 cm, in 0.5 cm increments.

Laser:

The lasers to be used for the procedure (Intermedic, Spain) are connected to the optical fibers, once the optical fibers are satisfactorily positioned within the flexible introduction catheters.

Light detection:

One light detecting probe will be placed in the rectum to ensure that the light dose is sufficiently low. The prostate is illuminated prior to drug injection and the light measured. If the light in the rectum exceeds 13 mW/cm² then the optical fibers in the prostate will be repositioned.

Drug delivery:

The infusion puncture site should be placed in a large vein at the top of the forearm. The infusion will be conducted using automatic syringes, through a fast flow peripheral line (antecubital catheter). The Sponsor will provide the study centre with the appropriate infusion devices. Infusion will be over 10 minutes. The choice for size of intravenous catheter will be left up to the discretion of the involved medical

team who will be responsible for ensuring that the catheter is flushed and working properly prior to starting infusion.

Light delivery:

The light delivery will begin once the drug infusion has ended. Light will be delivered at an energy dose of 200 J/cm with a power of 150 mW/cm over 22min 15s.

See appendix 6 "VTP procedure Book".

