#### **Light Density Index (LDI)**

The Light Density Index (LDI) is defined, for each zone to be treated, as the ratio of the cumulative length of illumination tip of the fibres (in cm) per cubic centimeter of the targeted zone. It is calculated as:

TI = (Total length of illumination tip of the fibre) / treatment volume

Where:

- The Total length of illumination tip of the fibre is the sum of the length of each illumination tip of the fibres used during the procedure for the treated lobe or quadrant. The volume of the targeted zone is calculated precisely by the prostate MRI conducted pre-treatment.
- An LDI equal or superior to 1.0 should be achieved for each zone to be treated.

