***Efficacy analysis***

All analyses will include the “efficacy population” as described above with a secondary analysis including patients undergoing retreatment at 3 months.

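### The primary analysis leaves out treated men whose drug, light or LDI delivery fell short, although the hypothesis is about all treated men

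*SAP*

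**What the plan says.** The Synopsis of the protocol states the hypothesis that the treatment "will result in the absence of detectable, clinically significant prostate cancer in over 70% of treated men". Protocol section 10.2.2.4 defines an intention-to-treat set, which ignores protocol deviations, and a per-protocol set, which requires the appropriate drug dose, LDI and energy. Section 10.3, on the primary endpoint, assigns neither set to the primary test.

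The SAP has a safety population, used for safety endpoints, and one efficacy population. To be in the latter a man must have "received the appropriate dose of TOOKAD® Soluble, LDI and energy delivered and underwent the VTP procedure", and must also have "had no major protocol deviations and provided data at the 12 month biopsy". The SAP's Efficacy analysis section then says: "All analyses will include the “efficacy population” as described above". The only other efficacy analysis named there concerns men retreated at 3 months. No intention-to-treat or all-treated efficacy set is defined, and nothing is listed under the SAP's heading for changes from the protocol.

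On delivery, protocol section 5.5.5 says: "The drug or light administration can be discontinued at any time by the investigator in case of a significant adverse event (AE"). The LDI requirement is worded as a target in the SAP: "An LDI equal or superior to 1.0 should be achieved for each zone to be treated". Protocol section 2.2.4 reports that phase II studies "have shown a correlation between the total energy delivered and efficacy results".

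**The concern.** A delivery shortfall arises once treatment is under way, so it is part of what happens to a treated man. Under the SAP such a man leaves both numerator and denominator. The rule that a missing Month 12 biopsy counts as failure does not cover him, because he may have a biopsy. The rule that early grade 4 or 5 disease followed by radical therapy counts as failure does not put him back into the population.

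The delivery criterion is also loose. The SAP gives no numeric limit for an appropriate dose or energy, and no date by which the judgement must be made. Adjudication before the 12-month biopsy is required only for major deviations. The volume in the LDI comes from the TRUS software in protocol section 6.2.4 but from the pre-treatment MRI in the SAP, so who falls below 1.0 depends on which applies.

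At stake is what the headline rate means. It would be the response given adequate delivery, tested against 70% in a single-arm trial with no comparator to absorb a selection effect.

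**Working it through.** **Inputs.** Null rate 70%, assumed true rate 83.6%, one-sided alpha 10%, N = 44 (SAP, Planned sample size). Success if the one-sided 90% lower bound, rounded to 0.01, is at least 70%, which the SAP translates as 35 or more of 44 (SAP, Primary efficacy analysis). Planned number treated 50, for at least 44 evaluable (protocol Synopsis). The number of under-delivered men, k, is not given. I take k = 0 to 6, since 50 − 44 = 6. This range is an assumption.

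**Formula.** Exact (Clopper-Pearson) lower bound for x responders of n: L = the 10th percentile of Beta(x, n − x + 1).

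**Reproducing the SAP rule.** 35/44 = 79.5%, L = 0.696, which rounds to 0.70: success. 34/44 gives L = 0.672: failure. The cut-off of 35 reproduces. Its exact type I error at 70% is 10.9% and its power at 83.6% is 82.6%.

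**Putting excluded failures back.** Hold the responders fixed and add under-delivered men with grade 4 or 5 at Month 12.

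| Added failures | Start at the boundary (35/44) | Start near the design rate (0.836 × 44 = 36.8, so 37/44) |
|---|---|---|
| 0 | 35/44, L 0.696, success | 37/44, L 0.747, success |
| 1 | 35/45, L 0.678, failure | 37/45, L 0.727, success |
| 2 | 35/46, L 0.662, failure | 37/46, L 0.709, success |
| 3 | 35/47, L 0.645, failure | 37/47, L 0.691, failure |

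**Chance of a wrong success.** Let the true response among all 50 treated men be exactly 70%, an expected 35 responders. If excluded men respond at rate q, the men left in respond at (35 − qk)/(50 − k). Applying the SAP's rule to n = 50 − k:

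| k | Needed | q = 0 | q = 50% | q = 70% |
|---|---|---|---|---|
| 0 | 40/50 | 7.9% | 7.9% | 7.9% |
| 1 | 39/49 | 13.3% | 10.3% | 9.2% |
| 2 | 38/48 | 21.1% | 13.2% | 10.7% |
| 3 | 38/47 | 20.4% | 9.5% | 6.7% |
| 6 | 35/44 | 58.8% | 20.1% | 10.9% |

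The last column moves only because the cut-off is a whole number. When excluded men respond like the others, the error stays near the nominal 10%. The inflation comes entirely from excluded men doing worse.

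**Effect of the fix on power.** With all 50 analysed, success needs 40 (40/50, L = 0.709; 39/50, L = 0.687). If fully delivered men respond at 83.6% and k under-delivered men all fail, power is 81.3% (k = 0), 72.4% (1), 61.3% (2), 48.5% (3) and 13.1% (6).

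**The case against.** The strongest reply is that a restricted set was always intended. The protocol treats 50 men to obtain 44 evaluable, sizes the trial on fully evaluable data, and uses the same delivery criteria for its per-protocol set. Its intention-to-treat set is named for descriptive statistics only. This stands in part: a reader might infer that the SAP overrides a protocol intention-to-treat primary analysis, and it does not. But the protocol nowhere defines evaluable as fully delivered, and the hypothesis was not reworded to match a restricted set.

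A reader might also infer that other procedural rules push men below an LDI of 1. If rectal light is too high, "then the optical fibers in the prostate will be repositioned", and a 5 mm margin to the rectal wall, apex and urethra must be kept. The documents do not support that inference. LDI is total tip length divided by treatment volume, and moving a fibre changes neither. Energy is set per centimetre of fibre, and the rectal light check comes before drug injection. The margin is built into the planning software, and no text says it prevents an LDI of 1. Early stopping for an adverse event is the one documented route to incomplete delivery, and its frequency is not given.

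Finally, the SAP asks for appropriate delivery, which need not exclude a man for a trivial shortfall. That is fair, but it makes the missing definition matter more. The SAP does summarise LDI and energy and lists data by subject, so shortfalls would be partly visible. Neither step puts those men into an efficacy estimate.

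**Conclusion.** The concern holds in a limited form. The only population for the primary analysis excludes treated men on an undefined delivery criterion that is met or missed after treatment starts, while the hypothesis concerns treated men and no all-treated efficacy result is planned.

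The exclusion plausibly raises the response rate. It would go too far to say that the excluded men are the ones who will fail, or that the bias must run one way. The reported correlation comes from phase II studies used to set treatment conditions and does not predict the outcome of an individual man just short of target.

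The size cannot be known from the documents. One excluded failure overturns a result at the boundary; three are needed at about the design rate. Those figures assume that the excluded men have grade 4 or 5 at Month 12, and k is assumed throughout.

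**What to change.** In the SAP, define the primary efficacy set as all eligible men in whom infusion or illumination was started, whatever dose, LDI or energy was delivered, and keep the full-delivery set as a supportive per-protocol analysis. If the sponsor prefers to keep the present primary set, report the all-treated result next to it under the same success rule.

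In either case:

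- Define numerically what counts as appropriate delivery for the per-protocol set, and require the classification to be fixed before the Month 12 biopsy.
- Tabulate the men with LDI below 1, incomplete light or interrupted infusion, with their Month 12 result.
- Reconcile the source of the LDI volume between protocol section 6.2.4 and the SAP, since it decides who is excluded.
- Record the choice of population under the SAP's heading for changes from the protocol.

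The cost is SAP wording and one additional table; the technical delivery data are already in the VTP report form (protocol section 11.2). The headline rate may be slightly lower, and power falls if shortfalls occur and those men fail, as shown above. No treatment rule changes.
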